12.3.3 Reporting procedures for SUSARs

The chief investigator will report all SUSARs to the ethical committee(s) within required timelines. The chief investigator will also inform all investigators concerned of relevant information about SUSARs that could adversely affect the safety of participants. In addition, the chief investigator will report any SUSARs relating to licensed products used in the trial (ciprofloxacin) to the Medicine and Healthcare products Regulatory Agency (MHRA) using the electronic 'Yellow Card' System.

All SUSARs and deaths occurring during the study will be reported to the sponsor. For all deaths, any autopsy reports and relevant medical reports will be made available for reporting to the relevant authorities.

12.3.4 Procedures to be followed in the event of abnormal findings

Abnormal clinical findings from medical history, examination or blood tests, will be assessed as to their clinical significance. If a test is deemed clinically significant, it may be repeated, to ensure it is not a single occurrence. If a test remains clinically significant, the volunteer will be informed and appropriate medical care arranged as appropriate with the permission of the volunteer. Decisions to exclude the volunteer from enrolling in the trial or to withdraw a volunteer from the trial will be at the discretion of the Investigator.

12.3.5 Foreseeable medical occurrences

The following medical occurrences are foreseeable:

- Local sensation effects in the nose following inoculation.
- Local bruises following venesection
- Adverse reactions to ciprofloxacin as detailed in the Summaries of product characteristics (SmPC)

12.3.6 Adverse events of special interest

Adverse events of special interest will be reported as SAEs. These are:

- Severe hypersensitivity reactions to the inoculum (e.g. anaphylaxis)
- Overdosing of the inoculum

12.4 Safety profile review

The safety profile will be assessed on an on-going basis by the investigators.

12.5 Study committees

12.5.1 External Safety Committee (ESC)

An external safety committee will be appointed prior to recruitment.

The role of the ESC is to provide overall supervision for the trial and provide advice through its independent Chair. The ultimate decision for the continuation of the trial lies with the Chief investigator following advice from the ESC.

The ESC will be responsible for reviewing and assessing this protocol prior to commencement of the trial, recruitment, interim monitoring of safety and effectiveness, trial conduct and external data. The ESC will first convene prior to trial initiation and will then define the frequency of subsequent meetings (at least annually).

All correspondence between investigator and ESC will be conveyed by the investigator to the trial Sponsor. The study protocol and implemented safety procedures will be discussed with the ESC before starting the study.

The chair of the ESC may be contacted for advice and independent review by the investigator or trial Sponsor in the following situations:

- Following any SAE deemed to be possibly, probably, or definitely related to a study intervention.
- Any other situation where the Investigator or trial sponsor feels independent advice or review is important.

12.5.2 Ethics Committee

The study will be reviewed by the HRA. A progress report will be submitted to the REC 12 months after the date on which the favourable opinion on which the form was given.

13. Analysis and Statistical considerations

13.1 Endpoints of the study

Primary endpoint

- Rise in serological specific antibody titre comparing day 0 versus day 14 and 28 days post eradication and comparing early (day 4) versus late (day 14) eradication

Secondary endpoints:

- Assessment of colonisation – culture of *N. lactamica* from throat swabs at day 4 for group 1 and days 4, 7 and 14 for group 2
- Assessment of eradication – culture of *N. lactamica* from throat swabs on the day of eradication, one day, 10 days and 28 days after eradication
- Rise in mucosal specific antibody titre comparing day of screening versus day 14 and 28 days post eradication and comparing early (day 4) versus late (day 14) eradication
- Change in nasal cytokine profile comparing day 0 versus day 4, 14 and 28 days post eradication and comparing early (day 4) versus late (day 14) eradication
- Difference in environmental shedding between short (group 1) and longer (group 2) periods of colonisation.

Safety endpoints:

- Occurrence of unsolicited adverse events within the study period
- Occurrence of serious adverse events within the study period

Safety analysis will be carried out for all volunteers that received the inoculum, regardless of whether or not they complete the study.

13.2 Sample size

The previous experimental *N. lactamica* challenge study showed a significant rise in serological antibody titre against *N. lactamica* over 2 weeks (Deasy, Guccione et al. 2015). This gave SDs on a log-10 scale of 0.11 for IgA saliva and 0.26 for serum total IgG. For this study, using the SD of 0.26 we will be able to confirm a 4 fold rise with 10 carriers of *N. lactamica* with 90% power using analysis of variance.

Allowing for a drop out rate of approximately 10%, we will therefore recruit volunteers until we have 11 individuals colonised for each group up to a maximum of 22 volunteers for each group. At a dose of 10^4 colony forming units (cfu), long lasting colonisation with *N. lactamica* is easily induced in 35-65% of participants. We showed that increasing the inoculum to 10^5 cfu increased the subsequent carriage of *N. lactamica* to 50% (Evans, Pratt 2011). Therefore approximately 44 individuals will be enrolled. Assuming a screening failure rate of 5%, we will need to screen approximately 46 potential participants to achieve colonisation in 11 of each group.

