3.5 General overview

This study will compare the effect of short (4 days) versus longer (14 days) periods of nasal carriage of *N. lactamica* on immunogenicity and confirm the efficacy of oral eradication therapy with ciprofloxacin. Healthy adult volunteers will receive a nasal inoculation of *N. lactamica* and eradication therapy will be given on day 4 or 14. This information will be used to inform the design of future research into the colonisation kinetics and immunogenicity of related organisms. Specifically, the Medical Research Council has funded us to inoculate humans with genetically modified *N. lactamica*. Before designing the protocols for that study we need to know whether a short containment of the volunteers will be sufficient for immunogenicity, and how quickly we can discharge the volunteers after ciprofloxacin eradication. A wild-type strain of *N. lactamica* Y92-100 will be used for this study, selected because we have previously used it safely in experimental challenge of over 340 human volunteers. The same strain is the parent strain for the GMO work described above.

4. Objectives

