4.1 Primary objective

- To compare the effect of short (4 days) versus longer (14 days) oropharyngeal carriage on systemic and mucosal humoral immunogenicity following nasal inoculation with *Neisseria lactamica*

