5.3 Randomisation and blinding

There will be no randomisation or blinding in this study. Prior to enrolment volunteers can give their preference for early eradication at day 4, or late eradication at day 14. Once one group has reached 22 volunteers, any remaining volunteers will be recruited in the other group to ensure both arms include a maximum of 22 participants.

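### The stated 90% power for a 4-fold rise is not what 10 carriers per group deliver at SD 0.26, and section 13.2 gives no detectable difference for the short versus longer comparison

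*Combined protocol and SAP*

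**What the plan says.** The primary objective in section 4.1 is comparative: "To compare the effect of short (4 days) versus longer (14 days) oropharyngeal carriage on systemic and mucosal humoral immunogenicity". The primary endpoint in 13.1 has two parts, a rise in specific serum antibody from day 0 and a comparison of early with late eradication. Section 3.5 gives the practical purpose: "we need to know whether a short containment of the volunteers will be sufficient for immunogenicity".

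The sample size in 13.2 rests on an earlier challenge study by the same group: "This gave SDs on a log-10 scale of 0.11 for IgA saliva and 0.26 for serum total IgG". From this it concludes that "using the SD of 0.26 we will be able to confirm a 4 fold rise with 10 carriers of" the organism. The power claimed for this is 90%, and the method named is analysis of variance. After an allowance of about 10% for dropout, it says "we will therefore recruit volunteers until we have 11 individuals colonised for each group up to a maximum of 22 volunteers for each group". The 10 is therefore used as 10 per group.

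Section 13.2 states no alpha, no sidedness and no short versus longer difference. It does not say whether 0.26 is the SD of a titre or of a within-person change. Section 13.3 names Fisher exact and McNemar tests and does not mention analysis of variance.

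**The concern.** A 4-fold effect is more than two SDs at SD 0.26, so 10 carriers in each group should give power far above 90%. The one figure that justifies the sample size therefore does not fit the design it is attached to. The inputs needed to check it are missing.

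The figure is also expressed as a rise, whereas the primary objective is a difference in response between two durations of carriage. A reader who wants to know how large a deficit after short carriage the trial could detect will not find it. The 4-fold, 90% statement could be mistaken for that answer. This matters because the result is meant to inform how long volunteers are contained in later studies with the genetically modified organism.

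**Working it through.** **Inputs from 13.2.** Effect: log10(4) = 0.602. SD: 0.26 log10. n: 10 carriers, then used per group. Power: 90%, by analysis of variance.

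**Assumptions.** Two-sided 5%, because none is stated; 10 evaluable carriers in each group; normally distributed log10 values. With two groups, one-way analysis of variance is the two-sample t test.

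**Formulas.** Power is taken from the noncentral t distribution.
- Two groups of n: ncp = δ / (SD × √(2/n)), df = 2n − 2.
- One group, paired: ncp = δ / (SD / √n), df = n − 1.

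**Step 1: the plan's own figure.** The standardised effect is 0.602 / 0.26 = 2.32.

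| Reading | ncp | df | Power for 4-fold |
|---|---|---|---|
| Rise within one group, n = 10, SD of change 0.26 | 7.32 | 9 | >99.9% |
| Rise within one group, n = 10, SD of change 0.368 | 5.18 | 9 | 99.6% |
| Between groups, 10 v 10, SD 0.26 | 5.18 | 18 | 99.8% |
| Between groups, 5 v 5 (10 in total), SD 0.26 | 3.66 | 8 | 89.2% |
| Between groups, 10 v 10, SD 0.368 | 3.66 | 18 | 93.3% |
| Between groups, 9 v 9, SD 0.368 | 3.47 | 16 | 90.3% |

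The SD of 0.368 applies if 0.26 is the SD of a single titre and a person's two titres are uncorrelated: 0.26 × √2 = 0.368. At SD 0.26 the stated 90% is approached only with 5 per group.

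**Step 2: what 10 per group can detect between groups.** At n = 10 per group the difference detectable with 90% power is 1.534 SDs. The ratio of rises is 10^(1.534 × SD of change). If 0.26 is a titre SD and the within-person correlation is ρ, the SD of change is 0.26 × √(2(1 − ρ)).

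| What 0.26 represents | SD of log10 change | Ratio detectable at 90% | Power for a 2-fold ratio |
|---|---|---|---|
| SD of the change (or titre SD, ρ = 0.5) | 0.26 | 10^0.399 = 2.5 | 69% |
| Titre SD, ρ = 0 (assumed) | 0.368 | 10^0.564 = 3.7 | 41% |
| Titre SD, ρ = 0.75 (assumed) | 0.184 | 10^0.282 = 1.9 | 93% |

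**Step 3: precision of the short/long ratio.** The 95% CI half-width on the log10 scale is t(18) × SD × √(2/10), with t(18) = 2.101.
- SD 0.26: 2.101 × 0.26 × 0.447 = 0.244, so the estimate is multiplied and divided by 1.76.
- SD 0.368: 2.101 × 0.368 × 0.447 = 0.345, a factor of 2.2.

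**The case against.** The strongest defence is that the text can be read so that it nearly works. If 0.26 is a single-titre SD with uncorrelated repeats, 9 per group give 90.3% and 10 per group give 93.3%, which a loose claim of 90% would cover. With alpha 0.025 for two time points (also an assumption), the same SD gives 87.7% at 10 and 91.2% at 11 per group. This stands as far as it goes. It would be wrong to say that 90% can arise only from 10 carriers in total; that holds at SD 0.26 and two-sided 5%. But each rescuing reading depends on something the plan does not state.

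Three stronger inferences are tempting and not supported.
- **That the trial is underpowered for a 4-fold effect.** It is not. Every 10-per-group reading at two-sided 5% gives more than 90%.
- **That the power statement is purely within-group and off target.** The word rise suggests a within-group quantity, but analysis of variance and the 5 v 5 match leave a two-group calculation possible. The rise is also part of the primary endpoint, and the hypothesis in 6.6, seroconversion by day 14 in those colonised at day 4, is a within-person question for which power exceeds 99%.
- **That a non-significant difference will be taken as showing short carriage is sufficient.** No section gives that rule; 3.5 says only that the information will inform later research.

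The 2-fold scenario is illustrative. It does not come from the documents, and neither do the correlations.

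**Conclusion.** The point holds in a limited form. At SD 0.26 and two-sided 5%, the design gives 99.8% power for a 4-fold ratio between groups and over 99.9% for a 4-fold rise within a group, not 90%. The mismatch is harmless for a 4-fold effect and gives no reason to change the sample size.

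The substantive gap is that no detectable difference is stated for the comparison in the primary objective. At 90% power it is about 2.5-fold if 0.26 is the SD of the change. It ranges from 1.9-fold to 3.7-fold over the correlations tried, and those are not bounds. A true 2-fold deficit would be missed in about 31% of such trials at SD 0.26 (1 − 0.69) and 59% at SD 0.368 (1 − 0.41).

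These figures assume 10 evaluable carriers per group and address random error only. Allocation is by volunteer preference (5.3), so they do not cover bias between groups. Severity: should-fix.

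**What to change.** **Section 13.2.** State alpha and sidedness, say whether 0.26 is the SD of a titre or of a change, and say that 10 is per group. Replace the power sentence with, for example: *Ten carriers per group give 90% power (two-sided 5%) to detect about a 2.5-fold difference between groups in the rise from day 0 if the SD of the log10 change is 0.26; power for a 2-fold difference is 69%.* If 0.26 proves to be a titre SD, use the figures for the correlation in the earlier data: 3.7-fold and 41% at zero correlation, 1.9-fold and 93% at 0.75. Present these as detectable differences. They follow from the sample size and do not justify a margin of sufficiency.

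**Section 13.3.** For the titre endpoint, replace the Fisher exact and McNemar wording with a comparison of log10 change between groups by analysis of variance, as 13.2 assumes. Report the short/long ratio of rises with its 95% CI, and say that sufficiency will be judged from that interval and not from p > 0.05.

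**Cost.** Wording in two sections and a look-up of what 0.26 represents in the sponsor's earlier data. No added volunteers, visits or assays.

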Trial Centre	NIHR Wellcome Trust Clinical Research Facility, Southampton University Hospital NHS Foundation Trust, [name]
Trial Sponsor	RHM MED1354
Code	
Design	Phase II prospective controlled human Neisseria lactamica infection study
Population	Healthy volunteers aged 18-45 years
Sample size	Total up to 44 volunteers Group 1: Nasal inoculation with Neisseria lactamica with eradication on day 4 – up to 22 volunteers or until 11 colonised on day 4 Group 2: Nasal inoculation with Neisseria lactamica with eradication on day 14 – up to 22 volunteers or until 11 colonised on day 4
Follow up duration	Group 1: Challenge at day 0, eradication on day 4, follow up on days 5, 14 and 32 Group 2: Challenge at day 0, follow up on day 4 and 7, eradication on day 14, follow up on day 15, 24 and 42
Planned Trial Period	13/03/2017– 30/9/2018
Primary Objective	To compare the effect of short (4 days) versus longer (14 days) oropharyngeal carriage on systemic and mucosal humoral immunogenicity following nasal inoculation with Neisseria lactamica
Secondary Objective	To assess the efficacy of oral Ciprofloxacin in eradicating nasal Neisseria lactamica colonisation by 24 hours after treatment
Microbial challenge material	Neisseria lactamica Wild type – dose 100000 (10^5) cfu

2. Abbreviations

AE	Adverse Event
ALP	Alkaline Phosphatase
ALS	Advanced Life Support
ALT	Alanine transaminase
AR	Adverse Reaction
cfu	Colony Forming Unit
CRF	Case Report File
DSUR	Development Safety Update Report
ESC	External Safety Committee
GCP	Good Clinical Practice
GP	General Practitioner
HRA	Health Research Authority
ICH	International Conference on Harmonisation
ILS	Immediate Life Support
MHRA	Medicine and Healthcare products Regulatory Agency
NHS	National Health Service
NIHR	National Institute for Health Research
NIHR-WTCRF	NIHR Wellcome Trust Clinical Research Facility
Nlac	Neisseria lactamica
PBS	Phosphate Buffered Saline
PCR	Polymerase Chain Reaction
QA	Quality assurance
RBC/HPF:	Red blood cell per high power field
REC	Research Ethics Committee
SAE	Serious Adverse Event

SAR	Serious Adverse Reaction
SmPC	Summaries of Product Characteristics
SOP	Standard Operating Procedure
SUSAR	Serious Unexpected Serious Adverse reaction
TOPS	The Over-volunteering Prevention System
UAR	Unexpected Adverse Reaction
UHS NHS FT	University Hospital Southampton NHS Foundation Trust

3. Background and rationale

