5.2 Study volunteers

Healthy volunteers aged 18-45 years will be recruited and challenged until 11 volunteers in each group are colonised with *N. lactamica* at day 4 or up to a maximum of 44 volunteers in total. Based on our previous studies with *N. lactamica*, colonisation was achieved in 35% of *N. lactamica* -inoculated non-smokers at a dose of 10^4 cfu, (Deasy, Guccione et al. 2015) and increasing the inoculum to 10^5 cfu increased the subsequent carriage of *N. lactamica* to 50% (Evans, Pratt 2011). Therefore inoculating up to 44 participants will result in approximately 22 colonised individuals.

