6.6 The optimal and safe dose of the inoculum

Based on the previous *N. lactamica* work it is estimated that 50% of volunteers will be colonised 1-2 weeks after inoculation with 10^5 cfu without any safety concerns (Deasy, Guccione et al. 2015). The hypothesis is that those who are colonised at day 4 will exhibit seroconversion by day 14, confirming biologically 'significant' colonisation.

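### Section 13.2 states an expected yield as an achieved one: with 22 inoculated per group at 50%, the chance of 11 carriers in both groups is 34%, and the 50% is not a day-4 rate

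*Combined protocol and SAP*

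**What the plan says.** Section 13.2 starts from the analysis need: "we will be able to confirm a 4 fold rise with 10 carriers of *N. lactamica* with 90% power using analysis of variance". It adds about 10% for dropout and recruits "until we have 11 individuals colonised for each group up to a maximum of 22 volunteers for each group". With a colonisation rate of 50% at 10^5 cfu this gives about 44 enrolled. With 5% screening failure it then concludes that "we will need to screen approximately 46 potential participants to achieve colonisation in 11 of each group".

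The synopsis fixes when carriers are counted, using the same rule for both groups: "up to 22 volunteers or until 11 colonised on day 4". Section 5.2 also counts at day 4, "up to a maximum of 44 volunteers in total", and expects approximately 22 colonised. Section 5.3 moves later volunteers to the group still open, "to ensure both arms include a maximum of 22 participants".

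On the rate itself, section 6.6 says "it is estimated that 50% of volunteers will be colonised 1-2 weeks after inoculation". Section 3.4 adds that carriage is detectable by 1-2 weeks in 80-90% of those colonised, and that data on earlier detection are lacking.

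**The concern.** Two steps in section 13.2 do not follow.

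- The cap of 22 equals the target divided by the assumed rate, so the target is the mean of the carrier count and there is no margin. A count falls below its mean a large part of the time, and here two groups must both reach it. Nothing in the plan states the chance of success or what the study can detect with fewer carriers. Section 9.4 allows replacement of volunteers who withdraw, not of those who fail to become colonised.
- The rate belongs to 1-2 weeks, but the count is made on day 4. If carriage is harder to detect on day 4, the yield is lower than section 13.2 implies.

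At stake is whether the stated number of carriers, on which the power statement is built, is likely to be reached.

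**Working it through.** **Inputs.** Carriers needed: 10 per group. Dropout: about 10%. Target: 11 per group. Cap: 22 per group. Colonisation rate: 50%. Screening failure: 5%. SD: 0.26 on the log10 scale. All are in section 13.2; the day-4 count is in the synopsis and section 5.2.

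**The plan's own figures.** 10/(1 - 0.10) = 11.1, taken as 11. 11/0.50 = 22 per group, so 44 in total. 44/0.95 = 46.3, stated as about 46. All reproduce.

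**Chance of reaching the target.** Let X be the number of day-4 carriers if all 22 in a group are inoculated, X ~ Binomial(22, p). Closing a group at 11 does not change the chance of getting there within 22. The groups are treated as independent, so the chance for both is the square of the chance for one.

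At p = 0.50 the mean is 22 × 0.50 = 11.

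- P(X ≥ 11) = 0.584 in one group; 0.584² = 0.341 in both.
- P(X ≥ 10) = 0.738 in one group; 0.738² = 0.545 in both, before dropout.

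**Other day-4 rates.** The documents give no day-4 rate, so these values of p are assumptions:

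| Day-4 rate | Mean carriers of 22 | At least 11: one group / both | At least 10: one group / both |
|---|---|---|---|
| 40% | 8.8 | 23% / 5% | 38% / 14% |
| 45% | 9.9 | 40% / 16% | 57% / 32% |
| 50% | 11.0 | 58% / 34% | 74% / 55% |
| 55% | 12.1 | 75% / 57% | 87% / 75% |
| 60% | 13.2 | 88% / 77% | 94% / 89% |

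An 80% chance of 11 in both groups needs a day-4 rate of about 61%. The 40% and 45% rows are what would follow if 80-90% of an eventual 50% were detectable on day 4 (0.8 × 0.5 and 0.9 × 0.5). That borrows the 1-2 week detection figure and is only illustrative.

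**What a shortfall costs.** The plan states neither the significance level nor which quantity the 0.26 describes. Assume two-sided 0.05, a two-sample t-test and 0.26 as the SD of the rise. Solving the noncentral t power for 90% gives this detectable between-group ratio:

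| Carriers per group | 6 | 7 | 8 | 9 | 10 | 11 |
|---|---|---|---|---|---|---|
| Ratio | 3.5 | 3.1 | 2.8 | 2.7 | 2.5 | 2.4 |

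For a 4-fold difference (log10 4 = 0.602) power is 89% with 5 per group, 95% with 6 and over 99% with 10. If 0.26 is instead the SD at a single visit and the two visits are independent (assumed), the SD of the rise is 0.26 × √2 = 0.368. Power for 4-fold is then 93% at 10, 86% at 8 and 72% at 6 per group, and the detectable ratio is about 3.7 at 10 and 5.8 at 6.

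**The case against.** The strongest reply is that the plan does not promise 11. The stopping rule has two limbs, 11 colonised or the cap, so reaching the cap first is foreseen, and section 5.2 speaks only of approximately 22 colonised. This stands, and it confines the fault to the last clause of section 13.2, which reads as an assurance. A planned fallback is still not a stated chance of needing it.

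Second, 11 already carries the dropout allowance, so 10 is the fairer target. That is why both are shown; 55% for both groups is still little better than even.

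Third, a shortfall may matter little. This largely stands for a 4-fold difference if 0.26 is the SD of the rise: at 50%, the chance of at least 6 carriers in both groups is 98%, and 6 per group gives 95% power. It stands less well if 0.26 is a single-visit SD, or if the difference of interest between 4 and 14 days of carriage is smaller than 4-fold.

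Some stronger readings are tempting but not supported:

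- *The numbers 44 and 46 are wrong.* They reproduce; only the conclusion drawn from them fails.
- *Sections 5.2 and 5.3 contradict each other on the cap.* 22 + 22 = 44, so they agree.
- *The per-group cap wastes volunteers.* A group that closes early leaves places unfilled; nobody is inoculated needlessly.
- *The day-4 rate is below 50%.* The documents say early data are lacking. That supports uncertainty, not a particular lower rate. The 35% for non-smokers in section 5.2 was at a tenfold lower dose.

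**Conclusion.** The point holds as a misstatement of what the sample size delivers. On the plan's own 50%, 11 carriers in both groups is more likely to be missed (66%) than met (34%); for 10 in both, before dropout, the chance is 55%. The rate is also applied to a day for which the documents have no data. Over assumed day-4 rates of 40% to 60%, the chance of 11 in both groups runs from 5% to 77%, so the true position could be much worse or considerably better.

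These probabilities assume independent volunteers, a common rate in the two groups and full use of the 22 places where needed. A reader might infer that the trial is underpowered. The documents do not support that: the effect of a shortfall depends on what the SD of 0.26 describes and on the size of difference of interest, and the plan settles neither for the comparison between groups.

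**What to change.** In section 13.2, replace the closing claim with wording such as: *With 22 inoculated per group and a day-4 colonisation rate of 50%, 11 carriers per group are expected on average. The probability of at least 11 is 58% in one group and 34% in both (74% and 55% for at least 10). For both groups it is 5% (14%) at a rate of 40%, 16% (32%) at 45% and 77% (89%) at 60%.* State that the 50% is a 1-2 week estimate and that no day-4 rate is available. Add the detectable difference for 6 to 11 carriers per group, with the significance level, the test and the meaning of the SD of 0.26 made explicit. The cost is wording, and a less favourable stated yield.

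Optionally, the sponsor may consider letting a group that reaches 11 pass its unused places to the other within the total of 44. At 50%, the chance of 11 in both groups then rises to at most P(Binomial(44, 0.5) ≥ 22) = 56%. The chance of 10 in both rises to about 67-70% by simulation with groups closing at 11; P(Binomial(44, 0.5) ≥ 20) = 77% would apply only if groups closed at 10. Both are best cases, because they need each day-4 result before the next inoculation, while section 11.2 allows up to 48 hours of culture and up to 24 hours of sub-culture. The costs are overriding volunteer preference for those who enter late, and unequal inoculated numbers. The restatement is needed whether or not this option is taken.

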N. lactamica (Nlac) has been shown to be safe in human challenge as we have found in over 340 volunteers experimentally inoculated with this organism (Evans, Pratt et al. 2011) (Deasy, Guccione et al. 2015). Even at a very low dose of 10^4 colony forming units (cfu), long lasting colonisation with Nlac is easily induced in 35-65% of participants. We showed (Evans, Pratt 2011) that increasing the inoculum to 10^5 cfu increased the subsequent carriage of *N. lactamica* to 50%. In 80-90% of those successfully colonised, this is detectable by 1-2 weeks. Data regarding earlier detection of colonisation is currently lacking. (Evans, Pratt et al. 2011) (Deasy, Guccione et al. 2015) Colonisation has a clear effect on the nasal mucosal microbiome, in that meningococcal acquisition is effectively inhibited in participants who carry the organism (Deasy, Guccione et al. 2015). Colonisation is immunogenic with an increase in specific serum IgG by 2 weeks and specific salivary IgA by 4 weeks (Evans, Pratt et al. 2011). No eradication therapy has previously been given following experimental inoculation but Ciprofloxacin has been shown to be effective in the eradication of *N. meningitidis* with clearance in 100% of previously colonised individuals after 24 hours. (Pugsley, Dworzack et al. 1987) To design future planned studies using *N. lactamica* nasal inoculation and colonisation in order to prevent invasive *N. meningitidis* disease, it is necessary to further evaluate the colonisation kinetics and efficacy of eradication following antibiotic treatment. Planned studies include infection with *N. lactamica* engineered to express antigens included in modern vaccines such as NadA and PorA. Such studies will require containment of volunteers and for ethical and economic reasons it will be necessary to make the period of colonisation as short as possible, and to eradicate carriage of the organism at the end of the experiment. Previous challenges we have done with *N. lactamica* have allowed the volunteers for prolonged periods of follow-up over 6 months.

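### The plan applies a 50% carriage rate dated 1-2 weeks after inoculation to a target set by culture on day 4, so it has no basis for stating that 44 inoculated will give 11 carriers per group; even at 50% the cap of 22 makes this a 34% chance

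*Combined protocol and SAP*

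**What the plan says.** The synopsis sets the size of each group as "up to 22 volunteers or until 11 colonised on day 4", and section 5.2 repeats the day 4 criterion. Section 5.3 caps each group at 22.

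The planning rate is 50% at 10^5 cfu. Section 6.6 gives its time point: "it is estimated that 50% of volunteers will be colonised 1-2 weeks after inoculation". Section 3.4 adds that 80-90% of those colonised are detectable by 1-2 weeks, and then: "Data regarding earlier detection of colonisation is currently lacking".

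Section 5.2 concludes: "Therefore inoculating up to 44 participants will result in approximately 22 colonised individuals". Section 13.2 asks for 10 carriers, raises this to 11 per group for about 10% dropout, and continues: "Therefore approximately 44 individuals will be enrolled". It then allows for 5% screening failure and states that "we will need to screen approximately 46 potential participants to achieve colonisation in 11 of each group".

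**The concern.** The rate and the target belong to different time points. Neither section 5.2 nor section 13.2 adjusts for this, and neither says that the day 4 rate is being taken as equal to the 1-2 week rate.

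Section 11.4 uses a looser definition of colonisation, any isolate from day 4 onwards, but this does not remove the problem. Group 1 receives eradication therapy on day 4 (section 10.1), and day 4 is its only colonisation assessment (section 13.1). A group 1 volunteer who would first have become culture-positive in the second week cannot be counted.

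Separately, 44 is the number at which the expected count equals the target. With a hard cap of 22 per group there is no margin for chance, so the target can be missed even if 50% is right.

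The number of carriers sets the precision of the comparison between short and longer carriage, which is the primary objective. The plan gives no detectable difference for a group that ends with fewer than planned.

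**Working it through.** **Inputs.** Carriage 50% (5.2, 6.6, 13.2); target 11 carriers per group (synopsis, 5.2, 13.2); cap 22 per group (5.3); dropout about 10%, screening failure 5% and SD 0.26 on the log10 scale (13.2). Assumed here: volunteers are independent, both groups share one day 4 rate, and tests are two-sided at 5% (the plan states no alpha).

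**1. The plan's own figures.** Inoculated: 22 / 0.50 = 44. Screened: 44 / 0.95 = 46.3, stated as about 46. Dropout: 10 / 0.9 = 11.1, stated as 11. The arithmetic reproduces, with 50% used as the day 4 rate.

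**2. Chance of reaching the target at a true 50%.** With X ~ Binomial(22, 0.50), P(X ≥ 11) = 0.584 for one group. For both groups: 0.584² = 0.341.

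**3. Expected carriers when recruitment stops at 11.** E[min(X, 11)] = 10.07 per group, against 11 planned. After 10% dropout without replacement: 10.07 × 0.9 = 9.1, against 10 planned.

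**4. Other day 4 rates.** The documents give no day 4 rate, so the rates below are scenarios and not estimates.

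| Assumed day 4 rate | Expected carriers among 22 | P(at least 11), one group | P(both groups) | Expected with stop at 11 | After 10% dropout |
|---|---|---|---|---|---|
| 30% | 6.6 | 0.039 | 0.2% | 6.6 | 5.9 |
| 40% | 8.8 | 0.228 | 5% | 8.6 | 7.7 |
| 50% | 11.0 | 0.584 | 34% | 10.1 | 9.1 |
| 60% | 13.2 | 0.879 | 77% | 10.8 | 9.7 |

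Solving P(X ≥ 11)² = 0.80 for the rate gives about 61%. That is the day 4 rate needed for an 80% chance that both groups reach 11.

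**5. Effect on the between-group comparison.** For a two-sample t-test with n per group, the noncentrality is δ / (0.26 × √(2/n)) on 2n − 2 degrees of freedom. Solving for 90% power, and then computing power at a 4-fold difference (δ = log10 4 = 0.602):

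| Evaluable carriers per group | Detectable log10 difference | Fold difference | Power at 4-fold |
|---|---|---|---|
| 10 | 0.399 | 2.5 | 99.8% |
| 8 | 0.454 | 2.8 | 99.0% |
| 6 | 0.541 | 3.5 | 95.0% |

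The plan does not say whether 0.26 is the SD of a change from baseline or of a single measurement. If the SD for the comparison were 0.26 × √2 = 0.37 (an assumption), power at 4-fold would be 93%, 86% and 72% for 10, 8 and 6 per group.

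**The case against.** The strongest reply is that an unknown day 4 rate is not a low one. A reader might infer that 44 inoculated should be expected to give fewer than 22 day 4 carriers. The documents do not show this. They contain no day 4 rate, carriage present on day 4 and later lost would act in the opposite direction, and section 13.2 quotes up to 65% even at the lower inoculum.

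Two tempting routes to a lower figure also fail:

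- **Multiplying 50% by the 80-90% in section 3.4, to get 40-45%.** If 50% is already the 1-2 week rate, this discounts it twice. If 50% is eventual carriage, the product is a 1-2 week rate. Neither is a day 4 rate.
- **Using the 35% reported for non-smokers, since smokers are excluded here.** That figure is at 10^4 cfu, and the smoking mix behind the 50% is not given.

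It is also fair to say that the plan writes of approximate numbers, that its rule is 11 carriers or the cap, so a shortfall is an allowed outcome, and that section 9.4 lets withdrawn volunteers be replaced and keeps their data for the primary objective. The flat 10% loss above is therefore the case without replacement. Finally, 6 per group still detects 3.5-fold with 90% power at SD 0.26, which is inside the 4-fold effect that the plan names.

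All of this stands, and it limits the severity. It does not supply the missing day 4 rate. Nor does it answer the 34%, which uses the plan's own rate and makes no claim that day 4 carriage is lower.

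**Conclusion.** The point holds in this form: the stated yield of 11 day 4 carriers per group from 44 inoculated and about 46 screened rests on an unstated assumption that the day 4 rate equals a rate dated 1-2 weeks after inoculation. The division is correct; the input is unsupported.

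If the 50% is granted, the chance of 11 carriers is 58% per group and 34% for both, and about 10.1 carriers per group are expected (9.1 after dropout without replacement). These figures assume independent volunteers and one rate for both groups.

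A reader might also conclude that the primary comparison would be underpowered. The documents do not support that for a 4-fold difference if 0.26 is the SD that applies to the comparison. The cost is a target that is likely to be missed in at least one group, and some loss of precision. This should be fixed; it is not a reason to hold the trial.

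**What to change.** In sections 5.2 and 13.2:

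- State that the day 4 carriage rate is unknown and that 50% is an assumption taken from a later time point.
- Replace the claim that about 46 screened will achieve 11 carriers in each group with the yield over a labelled range that includes 50%. For example, at 30%, 40%, 50% and 60%: 6.6, 8.8, 11.0 and 13.2 carriers expected among 22, with a 0.2%, 5%, 34% and 77% chance that both groups reach 11.
- Give the between-group fold difference detectable with 90% power at about 10, 8 and 6 evaluable carriers per group (2.5, 2.8 and 3.5), with the SD, alpha and sidedness stated.
- Use one definition of colonisation for the recruitment count in the synopsis and in sections 5.2, 11.4 and 13.2.

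The cost is the rewording of a few paragraphs and a less favourable stated yield. No extra volunteers and no change of procedure are needed.
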